2.4.4 Analyses of efficacy endpoints

Efficacy analyses will be performed on the mITT population using efficacy assessment collected during the study, including those obtained after IMP discontinuation or introduction of rescue therapy, unless otherwise specified.

For a patient to be included in a change from baseline analysis (endpoint – baseline) or a baseline adjusted analysis of an endpoint, the patient must have both a baseline and a post-baseline measure for that endpoint.

2.4.4.1 Analysis of primary efficacy endpoint(s)

The statistical test will be 2-sided tests at a nominal 5% significance level.

Primary analysis

The primary efficacy endpoint (change in HbA_{1c} from baseline to Week 26) will be analyzed using a mixed-effect model with repeated measures (MMRM) under the missing at random framework. The MMRM model will include treatment group (FRC or GLP-1 receptor agonist), randomization strata of HbA_{1c} (<8%, ≥8%) at V1 (week -2), randomization strata of GLP-1 receptor agonist subtype (QD/BID formulations, QW formulations) at screening, visit (week 8, week 12, week 18, Week 22 and Week 26), treatment-by-visit interaction and world region as fixed effects, and baseline HbA_{1c} value-by-visit interaction as the covariates. The adjusted mean change in HbA_{1c} from baseline to Week 26 for each treatment group will be estimated in the framework of this model, as well as the between group difference in LS means and the corresponding 95% CI.

The MMRM model will be implemented using SAS® (Version 9.4 or higher) MIXED procedure (PROC MIXED) with an unstructured correlation matrix to model the within-patient errors. Parameters will be estimated using the restricted maximum likelihood method with the Newton-Raphson algorithm. Denominator degree of freedom will be estimated using the Kenward-Roger approximation by fitting values from post-randomization scheduled visits in the 26-week randomized treatment period. This model will use only scheduled HbA_{1c} measurements.

Primary analysis will be performed using the mITT population and including all scheduled HbA_{1c} measurements collected during the study, including those obtained after IMP discontinuation or introduction of rescue therapy.

Sensitivity analyses

The following sensitivity analyses will be performed for the primary endpoint:

- The same MMRM model as described in the primary analysis will also be performed by including only the scheduled HbA_{1c} measurements collected during the 26-week on-treatment period (see [Section 2.1.3](#)).
- A sensitivity analysis will also be conducted on the 26-week completers in mITT population (ie, all mITT patients who completed the 26-week open-label randomized treatment period and did not start any rescue therapy before the end of the 26 week randomized treatment period) using the observed Week 26 values and the same MMRM model as described above.
- To investigate the impact of rescue therapy, the same MMRM model as described in the primary analysis will be performed by excluding the measurements after receiving the rescue therapy. The analysis includes all scheduled measurements obtained during the 26-week randomized treatment period, including those obtained after IMP discontinuation, but excluding those obtained after introduction of rescue therapy.
- In order for patients with missing data to be adequately represented by the patients with data, a sensitivity analysis using multiple imputations with respect to jump to control under the MNAR assumption will be performed. In particular,

- For patients in the GLP1-RA group who have no HbA1c values at Week 26, the missing data will be considered as missing at random. Missing HbA1c values in this situation will be imputed by the regression method using the observed data from GLP-1 RA group. The regression imputation model will include baseline HbA1c values and randomization strata.
- For patients in the FRC group who have no HbA1c value at Week 26, the missing HbA1c values will be imputed using baseline HbA1c values, randomization strata and coefficients generated from the regression model in the GLP-1 RA group plus an error. The error term will be randomly drawn from normal distribution with mean zero and a standard deviation. The standard deviation of the normal distribution will be calculated from pooled standard error of the regression model in the GLP-1 RA group and the standard error of the regression model in the FRC group. The regression model in the FRC group will be generated using the observed data from FRC group and will include baseline HbA1c values and randomization strata.

Missing HbA_{1c} values at Week 26 will be imputed 100 times to generate 100 data sets with complete HbA_{1c} values at Week 26. The change from baseline to Week 26 will be derived from observed and imputed HbA_{1c} values at this time point. The completed data sets will be analyzed using an ANCOVA model with treatment groups, randomization strata, and world region as factors and the baseline HbA_{1c} value as a covariate. The results from the 100 analyses will be combined using SAS PROC MIANALYZE.

Assessment of treatment effect by subgroup

Descriptive analyses will be performed on the primary endpoint to summarize the treatment effects across subgroups defined by the following baseline or screening factors:

- Race (American Indian or Alaska Native, Asian/Oriental, Black, Native Hawaiian or Other Pacific Islander, White, Other) (any category with less than 5 patients may be combined with another category as appropriate);
- Ethnicity (Hispanic or Latino, Not Hispanic or Latino);
- Age group (<50, ≥50 to <65, ≥65 to <75, ≥75 years of age) (any category with less than 5 patients may be combined with another category as appropriate);
- Gender;
- Baseline BMI level (<30, ≥30 kg/m²);
- GLP-1 receptor agonist subtype (QD/BID formulations, QW formulations) at screening
- Baseline HbA_{1c} (<8%, ≥8%);
- Pioglitazone use (Yes, No) at screening;
- SGLT2 inhibitor use (Yes, No) at screening (if each category contains sufficient number of patients);
- World region.

- Country

The treatment effects across the subgroups defined for each of these factors will be estimated for the change from baseline to Week 26 in HbA_{1c} in the mITT population, and using the MMRM approach with treatment group (FRC or GLP-1 receptor agonist), randomization strata of HbA_{1c} (<8%, ≥8%) at V1 (week -2), randomization strata of GLP-1 receptor agonist subtype (QD/BID formulations, QW formulations) at screening visit, subgroup factor, treatment-by-visit, treatment-by-subgroup factor, visit-by-subgroup factor, treatment-by-visit-by-subgroup factor, and world region as fixed effects, and using the baseline HbA_{1c} value-by-visit interaction as a covariate. The adjusted estimates of treatment mean differences (FRC versus GLP-1 receptor agonist) with standard errors and 95% CIs will be provided as appropriate across the subgroups.

In case that the subgroup factor is identical or similar to a randomization strata factor (eg, baseline HbA_{1c} category and GLP-1 RA category), only the subgroup factor will be included in the model in order to avoid collinearity issue in the analysis. In case that the subgroup factor is country, the world region will not be included in the model.

A similar MMRM model will also be used to estimate the within-group treatment effect for the change from baseline to Week 26 in HbA_{1c} for the following subgroups:

- Anti-lixisenatide antibody status (positive, negative) at the end of 26-week treatment;
- Anti-insulin glargine antibody status (positive, negative) at the end of 26-week treatment;
- Anti-lixisenatide antibody concentration at the end of 26-week treatment: <lower limit of quantification (LLOQ), ≥ LLOQ to 100 nmol/L, > 100 nmol/L.

If the antibody measurement is not available at Week 26, the LOCF procedure will be used by taking the last available post-baseline antibody measurement as the value at Week 26.

The adjusted means for each treatment group will be provided across the subgroups as appropriate, as well as the associated standard errors and 95% confidence intervals.

Summary statistics at scheduled visits

Summary statistics (for screening value, baseline value, observed values, and observed changes from baseline) at scheduled visits (using OC) will be provided for each treatment group. The summary will include the number of observations, mean, SD, SE, minimum, median, and maximum. Graphical presentations will also be used to examine trends over time using mean values (±SE) and mean changes from baseline (±SE) at each of the scheduled visits (using OC). These analyses will be performed using efficacy assessments obtained during the 26-week randomized treatment period, including those obtained after IMP discontinuation or introduction of rescue therapy.

- Similar presentations will be provided for patients who have completed the 26-week treatment period. In addition, summary statistics tables will be presented using HbA_{1c} assessments obtained during the 26-week on-treatment period (see [Section 2.1.3](#)).

- Similar summary statistics and graphical presentations will also be provided for FRC group for the whole study period including the extension period.

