8.2.3 Rescue Therapy

In case **HbA1c is above 8% at Week 12 or later on**, the Investigator will receive an alert issued by the central laboratory and should ensure that no reasonable explanation exists for insufficient glucose control and in particular that there is no intercurrent disease which may jeopardize glycemic control (eg, infectious disease), that the treatments are given at the planned dose and compliance to treatment and diet and lifestyle is appropriate. HbA1c assessment should be scheduled at next visit (if next visit is a phone call, it should be replaced by an unscheduled visit at site) or within 4 weeks. If appropriate corrective action fails and if the repeated HbA1c remain above 8%, a rescue therapy should be considered according to the Investigator's judgment.

In the FRC arm:

- rescue therapy is recommended only if further dose titration is not possible, ie, the patient is already at the maximum daily dose of 60 units;
- rapid acting insulin (insulin- glulisine when available) is suggested and should be started as a single daily administration to be given at the main meal of the day (excluding breakfast);
- basal insulin is not allowed in the FRC arm.

In the GLP-1 RA arm:

- suggested rescue therapy is basal insulin at the investigator's discretion.

During the extension period, suggested rescue therapy is rapid acting insulin (insulin- glulisine when available) for all patients.

All assessments planned at the end of the randomized treatment visit (V28) are to be performed before initiating rescue therapy during the randomized treatment period. All assessments planned at the end of extension period treatment visit (V35) are to be performed before initiating rescue therapy during the extension period. After these assessments are completed and rescue therapy initiated, the patient will remain in the study and continue to administer the study treatment (including background therapy). The planned visits and assessments should be performed until the last scheduled visit. Patients receiving rescue therapy during the randomized treatment period and eligible for the extension period can continue it as required.

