8.3 BLINDING PROCEDURES

8.3.1 Methods of blinding

This study is an open-label design.

Compensation for lack of blinding:

The Investigator and the Sponsor will not have access to the data of the primary efficacy endpoint (ie, HbA1c) nor to the data of the standardized meal test endpoints obtained after baseline visit until the end of the study. However, the study team may review the data for the primary efficacy

parameter in descriptive statistics with the name of the IMP treatment masked during data review meetings.

ARAC, and PSAC members will review and adjudicate events in a blinded manner (please also refer to [Section 6.4](#)).

Refer to [Section 10.5](#) for suspected unexpected adverse drug reaction unblinding by the Sponsor.

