10.3.4 Handling of patients after permanent treatment discontinuation

Patients will be maintained in the study as much as possible and followed-up according to the study procedures as specified in this protocol (except for the 3 day safety post-treatment follow-up assessment) up to the scheduled date of study completion, or up to recovery or stabilization of any AE requiring follow-up as specified in this protocol, whichever comes last.

If possible, after the permanent discontinuation of treatment regardless of the reason, the patients will be assessed as soon as possible using the procedure normally planned for the last dosing day

with the IMP (V28/End of randomized treatment visit for patients who discontinued the IMP before V28 (Week 26), or V35/end of extension treatment visit for patients who entered the extension period and discontinued the FRC before V35 (Week 52)).

For the meal test, please refer to [Section 9.2.1.2.2](#).

All cases of permanent treatment discontinuation should be recorded by the Investigator in the appropriate pages of the e-CRF and in the patient's medical records when considered as confirmed. IRT should be notified when a patient prematurely discontinues treatment.

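### The only not-at-random sensitivity analysis of HbA1c imputes Week 26 without the interim visits that the primary model uses, so a gap between the two results cannot be read as the effect of jump-to-control alone.

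*SAP*

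**What the plan says.** The primary analysis (SAP 2.4.4.1) is an MMRM under missing at random with an unstructured within-patient matrix and the factor "visit (week 8, week 12, week 18, Week 22 and Week 26". A missing Week 26 value is therefore informed by that patient's own earlier HbA1c.

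Four sensitivity analyses follow. Three are the same MMRM on restricted data or patients. The fourth is the only one labelled missing not at random. In it:

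- For controls without a Week 26 value, "the missing data will be considered as missing at random", but "The regression imputation model will include baseline HbA1c values and randomization strata", with no interim visit listed.
- The FRC rule borrows from that control model: "For patients in the FRC group who have no HbA1c value at Week 26, the missing HbA1c values will be imputed using baseline HbA1c values", together with strata and the coefficients of the control regression, plus an error term.
- The completed data go to an ANCOVA at Week 26 that also contains world region.

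Protocol 11.4.4.1 has the same text. No analysis in the text reviewed bridges the MMRM and this imputation. SAP Appendix C, the summary of analyses, was not part of that text.

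**The concern.** Missing at random means different things in the two analyses. The MMRM assumes it given baseline and the observed interim HbA1c. The imputation assumes it given baseline and strata only. If control patients leave because of their interim HbA1c, the first assumption can hold while the second fails.

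Imputing FRC drop-outs from the control model is the declared stress test. Discarding control data already collected is no part of that assumption, and the plan gives no reason for it.

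Other things change as well:

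- ANCOVA replaces MMRM.
- Region is in the analysis model but not in the imputation model.
- The rule in SAP 2.5.4 that re-allocates early-termination, pre-rescue and unscheduled measurements to the closest scheduled visit is stated only for parameters analysed by MMRM.

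At stake is how the stress test is read. A large gap could be blamed on jump-to-control when part of it is lost information. A gap near zero could be taken as robustness when two effects have cancelled.

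**Working it through.** **Plan's own figure.** SAP 1.3 gives SD 1.1, difference 0.4, 20% drop-out with no effect in FRC drop-outs, two-sided 5% and at least 90% power. The diluted difference is 0.8 × 0.4 = 0.32. With 250 per group, power is 90.2% (normal) or 90.1% (t-test), so the stated 250 is reproduced and is not in question. The planned SE of the difference is 1.1 × √(2/250) = 0.098.

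**Algebra.** Let D = -0.40 be the true Week 26 difference and p the share missing in each arm. Let r_C and r_F be the mean Week 26 residuals of the missing patients, relative to all patients of their own arm with the same baseline. Drop-outs are taken to have the same baseline distribution as the rest, so this is an approximation.

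- MMRM, if missing at random given interim HbA1c: D.
- Standard jump-to-reference (FRC drop-outs take control means but keep their own observed residuals): (1-p)D. The jump-to-control step is thus 0.40p: 0.04 at 10% missing, 0.08 at 20%.
- Plan. Observed controls have mean residual -p·r_C/(1-p), and every imputed patient in both arms inherits it. The control mean moves by -p·r_C/(1-p). The FRC mean relative to the true control mean is (1-p)D - p·r_F - p²·r_C/(1-p). The difference is (1-p)D + p(r_C - r_F).

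The omission therefore adds p(r_C - r_F). It vanishes if missingness is unrelated to interim HbA1c, and also if the dependence is equal in both arms. Its sign follows who leaves.

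**Size by simulation.** These inputs are assumptions; the documents give none of them: 600,000 patients per arm, SD 1.1, baseline correlation 0.5, residual correlation 0.6 or 0.85 per 4 weeks, and drop-out by logit on the last HbA1c with slope 0.5 or 1 per SD. Drop-out is either spread over the intervals after Week 8 or falls entirely after Week 22 (late). Strata and region are left out.

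Shift, plan minus jump-to-reference, with dependence in the control arm only and poorly controlled patients leaving (slope 0.5 / slope 1):

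| Missing | 0.6, spread | 0.6, late | 0.85, spread | 0.85, late |
|---|---|---|---|---|
| 5% | 0.006 / 0.012 | 0.012 / 0.022 | 0.014 / 0.025 | 0.017 / 0.032 |
| 10% | 0.012 / 0.023 | 0.022 / 0.041 | 0.025 / 0.049 | 0.031 / 0.059 |
| 20% | 0.022 / 0.043 | 0.038 / 0.070 | 0.048 / 0.089 | 0.055 / 0.100 |

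Estimates at 10% missing, correlation 0.85, spread:

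| Dependence on interim HbA1c | Missing at random with interim data | Jump-to-reference | Plan |
|---|---|---|---|
| None | -0.400 | -0.360 | -0.360 |
| Controls only, slope +1 | -0.400 | -0.360 | -0.312 |
| Controls only, slope -1 | -0.403 | -0.362 | -0.411 |
| Equal in both arms (arm-centred), slope +1 | about -0.40 | -0.360 | -0.359 |

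In the second row the total gap is 0.400 - 0.312 = 0.088. Of this, 0.040 is jump-to-control and 0.048 (55%) is dropped information; the algebra implies r_C of about 0.48. In the third row the omission (-0.411 + 0.362 = -0.049) more than cancels the penalty of 0.041, so the stress test appears to cost nothing.

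**The case against.** **The shift needs dependence that differs between arms.** This stands. No passage gives a reason to expect it in controls alone. Under equal arm-centred dependence the plan behaves as intended. If the same rule acts on actual rather than arm-centred HbA1c in both arms (correlation 0.85), the shift from jump-to-reference is only 0.002 to 0.023.

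**Few values should need imputing.** This largely stands. After rescue, "the patient will remain in the study and continue to administer the study treatment". After stopping treatment, "Patients will be maintained in the study as much as possible and followed-up according to the study procedures as specified in this protocol". Drop-out driven by HbA1c is further limited by masking: "The Investigator and the Sponsor will not have access to the data of the primary efficacy endpoint", although above 8% from Week 12 "the Investigator will receive an alert issued by the central laboratory". The 20% in SAP 1.3 refers to stopping treatment, so it is an upper figure for missing Week 26 values. At 5% missing the shifts are 0.006 to 0.032, at most a third of the SE.

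**A baseline-only, Week 26-only imputation is coherent and fully specified.** It is, and ignoring on-treatment values suits an immediate jump for FRC patients. That does not explain dropping interim values for controls, whose data are declared missing at random. It does show that the control arm must not be changed alone: with slope 1 in both arms and 10% missing, doing so gives -0.414 against -0.360 for jump-to-reference.

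**Stronger readings.** A reader might infer that the plan is biased against FRC, or tilted towards it. The documents support neither: the sign depends on which controls leave, and nothing in them says. Nor does this undermine the primary result. The primary MMRM, its alpha and the testing hierarchy do not use this imputation.

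**Conclusion.** The point holds as a matter of interpretation. As written, the one not-at-random analysis cannot isolate the assumption that it is meant to test. The dropped interim data may contribute about 0.01 to 0.10 HbA1c points in either direction, up to roughly one planned SE. With poorly controlled controls leaving, that is some 20-60% of the gap from the primary result. This rests on assumed correlations and slopes, 5-20% missing, and dependence in the control arm only. Otherwise the effect may be nil. The change to ANCOVA, the handling of region and the re-allocation rule add further differences that were not quantified. It is a worthwhile, inexpensive improvement and not a defect in the primary analysis.

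**What to change.** In SAP 2.4.4.1, with Protocol 11.4.4.1 aligned, and before the randomized-period database is locked:

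- Impute missing control values by sequential regression on baseline HbA1c, strata and Week 8, 12, 18 and 22 HbA1c.
- Impute FRC values by standard jump-to-reference with the same covariates: control-arm means and regression, with each patient's observed residuals retained. Change both arms together. State this target, because assuming instead that FRC drop-outs resemble controls with the same baseline gives different numbers.
- Add one missing-at-random multiple imputation with the same covariates, the same Week 26 definition (including re-allocation) and the same ANCOVA. Comparing it with the MMRM shows the technical changes. Comparing it with jump-to-reference shows the assumption alone.

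The cost is wording and minor extra programming on HbA1c already collected. No patients, visits or procedures are added.

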2.4.4.2 Analyses of secondary efficacy endpoints

For secondary efficacy endpoints included in the multiplicity procedure described in [Section 2.4.4.3](#), 2-sided statistical tests for the superiority of FRC over GLP-1 receptor agonist will be performed at the alpha level of 0.05.

Except for 2-hour PPG and glucose excursion, all continuous secondary efficacy endpoints at Week 26 defined in [Section 2.1.3.2](#) will be analyzed using the same MMRM approach as described in [Section 2.4.4.1](#) to compare FRC with GLP-1 receptor agonist. The analyses include all scheduled measurements collected during the 26-week randomized treatment period, including those obtained after IMP discontinuation or introduction of rescue therapy. This model will include fixed effect terms including treatment group (FRC or GLP-1 receptor agonist), randomization strata of HbA_{1c} (<8%, ≥8%) at V1 (week -2), randomization strata of GLP-1 receptor agonist subtype (QD/BID formulations, QW formulations) at screening, scheduled visit, treatment-by-visit interaction, and world region, and the covariate of baseline value-by-visit interaction. Means and adjusted means of each treatment group will be provided, as well as adjusted mean and associated two-sided 95% CI of the differences between treatment groups. The statistical tests for between-group differences will be two-sided at the alpha level of 0.05.

2-hour PPG and glucose excursion, for which only 1 post-baseline assessment is scheduled, will be analyzed using ANCOVA with the missing data at Week 26 imputed by LOCF to compare FRC with GLP-1 receptor agonist. This model will include fixed effect terms including treatment group (FRC or GLP-1 receptor agonist), randomization strata of HbA_{1c} (<8%, ≥8%) at V1 (week -2), randomization strata of GLP-1 receptor agonist subtype (QD/BID formulations, QW formulations) at screening, and world region, and a covariate using the corresponding baseline value. Means and adjusted means of each treatment group will be provided, as well as adjusted mean and associated two-sided 95% CI of the difference between treatment groups. The LOCF procedure will be used by taking the last available post-baseline measurement collected during the 26-week randomized treatment period as the value at Week 26.

Summary statistics (for screening value, baseline value, observed values, and observed changes from baseline) at scheduled visits (using OC) will be provided for each treatment group for continuous secondary efficacy endpoints. Each summary will include the number of observations, mean, SD, SE, minimum, median, and maximum. Graphical presentations will also be used to examine trends over time using mean values (±SE) and mean changes from baseline (±SE) at each of the scheduled visits (using OC).

All categorical secondary efficacy endpoints defined for 26-week randomized treatment period in [Section 2.1.3.2](#) will be analyzed using a Cochran-Mantel-Haenszel (CMH) method stratified on randomization strata of HbA_{1c} (<8%, ≥8%) at visit 1(week -2) and randomization strata of GLP-1 receptor agonist subtype (QD/BID formulations, QW formulations) at screening. The proportion in each treatment group will be provided, as well as the difference of proportions between groups

with associated 2-sided 95% CI. For the categorical secondary endpoints in which HbA1c is assessed at Week 26, all values at Week 26 will be used to determine whether a patient is a responder or not, even if they are measured after IMP discontinuation or introduction or rescue therapy. If no assessment is available at Week 26 at all, patients will be treated as failures (non-responders).

For HbA1c responders ($\leq 6.5\%$, $< 7\%$), summary tables and graphs will be provided by treatment group at scheduled visits (using OC). For between-group comparison, a sensitivity analysis will be performed excluding patients whose HbA1c values at baseline are $\leq 6.5\%$ (for the $\leq 6.5\%$ responder analysis) or $< 7\%$ (for the 7% responder analysis). The summary by visit may also be provided excluding those patients.

A KM curve will be provided by treatment group for the cumulative incidence of rescue therapy during the 26-week randomized treatment period and during the whole study period including the extension period (FRC group only). A listing will be provided for rescued patients.

For all continuous secondary endpoints, only descriptive statistics will be provided for the FRC group at the scheduled visits for the whole study period including the extension period. For all the categorical secondary endpoints defined for the extension period, counts and percentages will be summarized for FRC group using all data available at Week 52, with patients having data missing at Week 52 treatment as non-responders.

Sensitivity analysis

Sensitivity analyses will be performed for the following variables using scheduled measurements collected during the 26-week on-treatment period (excluding those collected after introduction of rescue therapy) (see [Section 2.1.3](#)). Continuous variables will be analyzed using MMRM or ANCOVA depending on the variables as specified earlier in [Section 2.4.4.2](#). Categorical variables will be analyzed using CMH method as described earlier. For the categorical variables in which HbA1c is assessed at Week 26, patients will be treated as failures (non-responders) if they have no assessment during the on-treatment period, including those who discontinue study treatment before Week 26, start rescue therapy before Week 26, or have no on-treatment assessment at all in mITT population.

- Change in 2-hour PPG and in glucose excursion during the standardized meal test from baseline to Week 26,
- Change in the daily average of the 7-point SMPG from baseline to Week 26 (each time point and average daily value),
- Change in FPG from baseline to Week 26,
- Change in body weight from baseline to Week 26,
- Percentage of patients reaching HbA1c $\leq 6.5\%$ at Week 26,
- Percentage of patients reaching HbA1c $< 7\%$ at Week 26.

